For Aim 2, the outcome of interest for this aim is having a skin examination (yes/no) assessed at the 6- and 12-month follow-up visits for our white, non-Hispanic population and at 3 and 9 month follow-up visits for our H/L population. This outcome will be a composite of examinations performed by a clinician (e.g. primary care doctor or dermatologist; Section A, Q11) or those completed by oneself or one’s partner (i.e. self-skin examination; Section A, Q13). We will tailor the suggested text of Q11 and Q13 given in Glanz et al. to fit our Aim and our timeline (Glanz et al. 2008). Q11 will be revised to read “In the past [time] months, have you had ...” (compared to “Have you ever had ...” as it currently reads). We will tailor the timeframe to correspond to the baseline, 6 or 12 month survey for our white, non-Hispanic population and at 3 or 9 month survey for our H/L population: at baseline the timeframe will be “in the past 12 months”; at the 6 and 12 month follow-up surveys, the timeframe will be “in the past 6 months” for our white, non-Hispanic population and “in the past 3 months” for our H/L population. In order to address the potential of a ceiling effect, we will ask participants who respond ‘yes’ to having had a skin examination in the past 6 months (white, non-Hispanic population) and 3 months (for our H/L population) the month and year of examination and whether the examination occurred at the Morsani Family Medicine or General Internal Medicine clinics. The outcome will be operationalized such that responding ‘yes’ to questions regarding completion of a skin examination by a clinician or by oneself or one’s partner will be considered a ‘yes’ response for skin examinations. Thus, this outcome is operationally a binary response (e.g., yes/no in the past 6 months (for our white, non-Hispanic participants) and in the past 3 months (for our H/L participants)) measured at the 6- and 12-month follow-up visits for our white, non-Hispanic population and at 3 and 9 month follow-up visits for our H/L population.

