For Exploratory Aim 3, the 12-item measure for children age 10 years or younger as reported by the study participant (Section B) will be used. Study participants with at least one child 10 years of age or younger will complete Section B, and those participants with more than one child within this age range are instructed to answer questions in this section thinking about the oldest child. Section B elicits responses about sun protection behaviors of the child, including number of red or painful sunburns over the past year for white, non-Hispanics and over the past 9 months for our H/L populations.

Since intermittent sunburns in adolescence are strongly associated with future melanoma risk (Armstrong et al. 1993, Gandini et al. 2005), the outcome of particular interest for our exploratory aim is the number of red or painful sunburns that lasted a day or more over the past timeframe. This outcome is measured by Section B, Q5, with a range of possible responses of 0 through 5 times (5 indicating 5 or more red or painful burns). We will tailor the timeframe to correspond to the baseline, 6 or 12 month survey for white, non-Hispanic participants and at baseline, 3 or 9 months survey for H/L participants).

STATISTICS

There will be no merging of data between the white non-Hispanic study population and

the H/L study population data. We will conduct mutually exclusive analyses within each of these two study populations.

Non-Hispanic study population

For our white, non-Hispanic population, the number of participants, 500 with high risk *MC1R* genotypes required to participate in this study was based upon the power calculations below.

Study power, Aim 1. We determined that randomizing 500 participants with high risk *MC1R* variants (250 each to the intervention and placebo arm) ensures 80% power to detect mean differences in hours of sun exposure of 0.17, 0.50 and 0.84, respectively, when the estimated standard deviation of the observed means is equal to 1, 3 and 5, respectively, when comparing participants with high risk genotypes who are randomized to intervention to participants with high risk genotypes who are randomized to placebo. These calculations are based on two-sided, alpha=0.05 level tests assuming a conservative auto-correlation equal to 0.1 to account for the repeated measures of participants over time, and a conservative 20% study attrition.

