Study power, Aim 2. We estimate a 20% incidence of having a skin examination within the past 12 months among participants on the placebo arm who received only standard risk and prevention information. We also conservatively estimate study attrition at 20%. Using these estimates, we determined that randomizing 500 participants with high risk *MC1R* variants (250 per study arm) ensures 80% power to detect an odds ratio of at least 1.8 when comparing participants with high risk genotypes who are randomized to intervention to participants with high risk genotypes who are randomized to placebo for the skin examination (yes/no) outcome. These calculations are based on two-sided, alpha=0.05 level tests and vary the proportion of skin examinations in the placebo group from 15-36% to be consistent with the range of possible values noted in the published literature.

Because we do not know the proportion of study participants who will have children 10 years of age or younger, we do not report study power for Aim 3 and consider this aim as exploratory at this time.

For our H/L populations the total number of participants, 400 with high risk *MC1R* genotypes (200 of whom will be recruited locally and 200 recruited in PR) required to participate in this study was based upon the power calculations below.

Hispanic/Latino study population

For our H/L populations the total number of participants, 400 with high risk *MC1R* genotypes (200 of whom will be recruited locally and 200 recruited in PR) required to participate in this study based upon the power calculations below.

Study power, Aim 1. Randomizing 400 participants with high risk *MC1R* variants (200 each to the intervention and control arm) ensures 80% power to detect mean differences in hours of sun exposure comparable to a small-medium effect size (Cohen's $d=30$),

when comparing participants with high-risk genotypes to intervention versus participants with high-risk genotypes randomized to control.

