Study power, Aim 2. We estimate a 20% incidence of having a skin examination with the past 9 months among control participants, with a range of 15% to 35%, and estimate study attrition of 20%. Using these estimates, we determined that randomizing 400 participants with high-risk *MC1R* variants (200 per study arm) ensures 80% power to detect an odds ratio of at least 1.95 to 1.73 when comparing participants with high-risk genotypes randomized to intervention versus those randomized to control for the skin examination (yes/no) outcome.

General approach. All analyses will be done within SAS, version 9 or later, primarily using PROC UNIVARIATE, FREQ and GENMOD. In the primary analyses, we will use an intention-to-treat (ITT) approach in which participants are analyzed in their randomized conditions regardless of the number of interventions or number of follow-up assessments they complete. Two-sided tests will be used for all hypotheses. We will assess the data for missing and out-of-range values with basic statistical procedures, including univariate statistics and graphs (histograms, box and whisker plots, scatter plots, and Q-Q plots). We will investigate data quality and integrity before any statistical modeling to ensure unbiased estimation.

The primary aim of this proposal is to test for significant ITT differences in the proportion of study subjects participating in skin prevention behaviors over the 12-month follow-up period by comparing those who receive a risk and prevention education intervention that includes feedback of *MC1R* genotype to those who receive a risk and prevention education session that includes only standard information. Our two primary outcomes of interests are (1) the average hours per week (weekdays and weekend) spent outside between 10am – 4pm; and (2) the completion of a full body skin examination for skin cancer (yes/no) by self, partner or clinician.

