Aim 2. Hypothesis testing for the binary outcome of full-body examination (yes/no) will follow the general analytic outline used in Specific Aim 1. This outcome will be modeled using the logistic framework of the GEE approach (i.e. specifying a logit link function), which properly accounts for the induced correlation from the repeated measures on participants over time, to assess ITT differences. These ITT differences comparing the probability of skin examinations will be presented as odds ratios with corresponding 95% confidence intervals where models will include main effects for intervention (standard risk and prevention plus genetic education versus standard risk and prevention education only), time (0, 6, and 12 months), and interaction term between the intervention and time. The interaction term will be used to test for possible differences in effects over time in the two study arms as the main test of interest. In addition, the logistic GEE model will contain baseline covariates and variables related to study participation and/or attrition as appropriate.

Exploratory Aim 3. We will use the GEE Poisson or ordinal regression models as appropriate with main effects for the intervention, time, and interaction term between the intervention and time, and will adjust for date of study enrollment to account for seasonality. Specifically, we are interested in estimating the intervention's efficacy in reducing the average number of red or painful sunburns in children.

All statistical analyses will be conducted by a member of the Biostatistics Core under the direction supervision of [name].

Analyses among individuals with low-risk *MC1R* genotypes will be conducted in a similar fashion to those detailed above. Because we do not expect to see ITT differences in prevention behaviors comparing those who receive a risk and prevention education intervention that includes feedback of *MC1R* genotype to those who receive a risk and prevention education session that includes only standard information among the low-risk group, power analyses are omitted.

Pilot study Aim 1. The overall prevalence of *MC1R* genotypes will be calculated with corresponding 95% confidence intervals.

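### The Aim 2 detectable odds ratios do not follow from their listed inputs: the Hispanic/Latino range of 1.95 to 1.73 is not reproduced, and the white non-Hispanic 1.8 cannot be traced

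*Combined protocol and SAP*

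**What the plan says.** All references are to the combined protocol and SAP.

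- **STATISTICS, Non-Hispanic study population.** The number of high-risk participants "required to participate in this study was based upon the power calculations below".
- **Study power, Aim 2 (white non-Hispanic).** "We estimate a 20% incidence of having a skin examination within the past 12 months among participants on the placebo arm". Attrition is put at 20%. From these estimates, 250 randomised per arm "ensures 80% power to detect an odds ratio of at least 1.8 when comparing participants with high risk genotypes who are randomized to intervention" with placebo. Tests are two-sided at 0.05, and the placebo rate is varied from 15% to 36%.
- **Study power, Aim 2 (Hispanic/Latino).** The control rate is 20% over 9 months (range 15% to 35%), with 20% attrition and 200 randomised per arm. From these, the design "ensures 80% power to detect an odds ratio of at least 1.95 to 1.73 when comparing participants with high-risk genotypes" between arms. No alpha is given.
- **Study power, Aim 1 (white non-Hispanic).** This calculation is described as "assuming a conservative auto-correlation equal to 0.1 to account for the repeated measures of participants over time". Neither Aim 2 paragraph gives a correlation.
- **Primary Outcome of the Study, Aim 2.** The response at each follow-up survey is binary ("yes/no in the past 6 months (for our white, non-Hispanic participants) and in the past 3 months (for our H/L participants").
- **STATISTICS, Aim 2.** The model is a logistic GEE with intervention, time and their interaction. The interaction is "used to test for possible differences in effects over time in the two study arms as the main test of interest".

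**The concern.** Each Aim 2 paragraph lists a control rate, an attrition rate and a number randomised, and presents its detectable OR as the result. The ordinary calculation with those inputs does not return the stated ORs.

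The listed rates also cover 12 and 9 months, while each survey asks about 6 and 3 months. They are therefore not the rates of the variable that the model will analyse.

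The high-risk sample size is said to rest on these calculations. As written, a reader cannot reproduce the 80% power. Nor can a reader tell which effect size, recall window or contrast it describes.

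**Working it through.** **Inputs.** White non-Hispanic: 250 per arm less 20% = 200 completers. H/L: 200 per arm less 20% = 160 completers. Two-sided 0.05 is stated for white non-Hispanic and assumed for H/L. Power is 80%.

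**Formula (single comparison, pooled variance).** p2 = p1·OR / (1 − p1 + p1·OR), and n per arm = [1.96·√(2p̄(1−p̄)) + 0.8416·√(p1(1−p1) + p2(1−p2))]² / (p2−p1)², where p̄ is the mean of p1 and p2.

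**Attempt to reproduce OR 1.8 at 20%.** p2 = 0.36/1.16 = 0.3103 and p̄ = 0.2552. Then n = (1.96 × 0.6165 + 0.8416 × 0.6116)² / 0.1103² ≈ 244 completers per arm, against 200 available. Power with 200 is Φ[(0.1103·√200 − 1.2084)/0.6116] = Φ(0.576) = 72%.

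**Single-comparison results.**

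| Population | Completers per arm | Control rate | Detectable OR | Power for the stated OR |
|---|---|---|---|---|
| White non-Hispanic | 200 | 15% | 2.02 | 63% (1.8) |
| White non-Hispanic | 200 | 20% | 1.91 | 72% (1.8) |
| White non-Hispanic | 200 | 36% | 1.77 | 83% (1.8) |
| H/L | 160 | 15% | 2.18 | 66% (1.95) |
| H/L | 160 | 20% | 2.05 | 74% (1.95) |
| H/L | 160 | 35% | 1.89 | 67% (1.73) |

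With 200 completers per arm, OR 1.8 reaches 80% power only from a control rate of about 29%. The H/L ORs of 1.95 at 15% and 1.73 at 35% need about 225 and 217 completers per arm. Both exceed the 200 randomised, so with no attrition at all the H/L range is still 2.02 to 1.77.

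**Two follow-up surveys averaged.** The effective n per arm is 2n/(1+ρ), with ρ = 0.1 borrowed from Aim 1. That gives 400/1.1 = 364 (white non-Hispanic) and 320/1.1 = 291 (H/L).

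The period rates must first be converted to the recall window. If windows are independent, the rate is 1 − (1 − P)^(1/k), with k = 2 for 12 to 6 months and k = 3 for 9 to 3 months. If windows share correlation 0.1 (beta-binomial), the rates are slightly higher. The ranges below span the two conversions.

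| Population | Period rate | Per-survey rate | Detectable OR |
|---|---|---|---|
| White non-Hispanic | 20% | 10.6-11.1% | 1.81-1.83 (77-79% power for 1.8) |
| H/L | 15% | 5.3-5.8% | 2.31-2.39 |
| H/L | 20% | 7.2-7.9% | 2.11-2.17 |
| H/L | 35% | 13.4-14.8% | 1.82-1.85 |

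Under the beta-binomial conversion, moving the correlation from 0 to 0.45 barely changes the H/L results: 2.30-2.31, 2.10-2.12 and 1.81-1.84.

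**What does approach the stated H/L range, with attrition applied.**

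- 15% and 35% used as per-survey rates need ρ = 0.42 and 0.48. At ρ = 0.45 they give 1.96 and 1.72. With ρ = 0.1 the range would be 1.81 to 1.61.
- Half-period (4.5-month) rates from 20% and 35%, namely 10.6% and 19.4%, give 1.96 and 1.73 at ρ = 0.1. The 15% end of the range (7.8%) gives 2.12.

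Neither set of rates matches a 3-month recall.

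**The white non-Hispanic 20% read as a per-survey rate.** At ρ = 0.1 the detectable OR is 1.63, and OR 1.8 keeps 80% power up to ρ of about 0.64.

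Every figure here compares arms at follow-up. None is for the intervention-by-time interaction.

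**The case against.** The strongest reply is that nobody planned a single comparison of completers. The outcome is measured twice, the analysis is a GEE, and the Aim 1 paragraph openly uses a repeated-measures correlation. Its detectable difference of 0.17 at SD 1 cannot come from one comparison of 200 per arm, which gives 2.80 × √(2/200) = 0.28. An unreported repeated-measures gain in Aim 2 is therefore plausible.

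For white non-Hispanic participants this largely stands. The 1.81-1.83 above assumes that all attrition occurs before the first survey. If half occurs by month 6 (an assumption: 225, then 200 per arm), the detectable OR at 10.6% is 1.80.

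For H/L it stands only as a possibility. One correlation near 0.45 almost fits both ends of the range, but that value is solved backwards from the answer. It also requires 9-month rates to serve as 3-month rates.

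Three stronger readings may tempt a reader, and the documents support none of them:

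- **The trial is underpowered, with true power of 72%.** The 72% belongs to a single comparison that is not the planned test, and power for the planned test cannot be computed from what is stated.
- **Attrition was forgotten.** All 250 per arm would give 1.79 at 20%, close to 1.8. The same omission does not produce the H/L range in a single comparison (2.02 to 1.77), and both paragraphs list attrition among their inputs.
- **The 1.8 is an arithmetic error.** A plausible unstated method comes within rounding of it.

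**Conclusion.** The stated Aim 2 ORs do not follow from the control rate, attrition and number randomised that are listed for them.

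- **H/L: firm.** The stated 1.95 to 1.73 compares with 2.18 to 1.89 in a single comparison of completers, 2.02 to 1.77 with no attrition, and about 2.3-2.4 to 1.8-1.85 with two surveys at 3-month rates. It is approached only with rates that do not match the recall window, in one case also with an unlisted correlation of about 0.42-0.48.
- **White non-Hispanic: untraceable, not shown to be wrong.** The detectable OR is 1.91 in a single comparison, and 1.81-1.83 with two surveys at 6-month rates.

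This rests on a two-sided alpha of 0.05 for H/L, a correlation of 0.1 carried over from white non-Hispanic Aim 1, the window conversions shown, and 1.95 and 1.73 belonging to 15% and 35%. The plan does not state that last pairing.

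**What to change.** In both Aim 2 power paragraphs, restate the detectable ORs after attrition, and give:

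- a per-survey control rate that matches the recall window (6 months for white non-Hispanic, 3 months for H/L);
- the within-person correlation;
- the alpha for H/L;
- the contrast to which the OR refers, either the intervention-by-time interaction or a time-averaged difference;
- which OR goes with which control rate.

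Replace the H/L range of 1.95 to 1.73 unless those stated inputs reproduce it. Single-comparison ORs may be shown only as a labelled reference, because they use 12- and 9-month rates and do not describe the planned test.

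The cost is a recalculation by the study statistician, who alone has the missing inputs, and new wording in two paragraphs. The restated figures may look less favourable. Participants, surveys and the outcome definition stay as they are.

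### The H/L Aim 1 power statement prints the effect size as d=30, and its 80% is not supported, even at d=0.30, once the plan's 20% attrition and planned test are applied

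*Combined protocol and SAP*

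**What the plan says.** In STATISTICS, Hispanic/Latino study population, Study power, Aim 1, the plan takes 400 high-risk participants, split evenly at 200 per arm, and claims that this number "ensures 80% power to detect mean differences in hours of sun exposure comparable to a small-medium effect size". A Cohen's d of 30 is printed for that effect. No alpha, attrition, standard deviation, correlation, visit or contrast is given there.

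Other sections supply some of these inputs:
- **Attrition.** The H/L Aim 2 power paragraph, on the same 400 people, takes a control proportion of 20% "with a range of 15% to 35%, and estimate study attrition of 20" percent. The Participant retention paragraph, which covers both populations, also gives 20%.
- **Sidedness.** The General approach paragraph says "Two-sided tests will be used for all hypotheses".
- **Alpha and correlation.** These appear only for the white, non-Hispanic Aim 1: "These calculations are based on two-sided, alpha=0.05 level tests assuming a conservative auto-correlation equal to 0.1".
- **Test.** The Aim 1 analysis paragraph plans a linear GEE with intervention, time and their interaction, and names the interaction as the main test. H/L surveys fall at baseline, 3 and 9 months.

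**The concern.** A difference of 30 standard deviations is not a small-to-medium effect, so the printed value cannot be right. Read as 0.30, the 80% still does not follow from 200 per arm with or without the 20% loss, and the sentence does not say which contrast the 0.30 describes.

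Hours outside between 10am and 4pm is one of two primary outcomes, and the protocol says that the 400 high-risk H/L participants were chosen from these calculations. This sentence is the only justification of the H/L sample for that outcome. If the H/L result is null, a reader would use it to judge which effect the trial could have excluded.

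**Working it through.** **Inputs.** From the documents: 200 per arm, 20% attrition, two-sided test, visits at 0, 3 and 9 months. Assumed: d = 0.30 (reading of the printed 30); alpha 0.05 and correlation 0.1 (both stated only for the other population); equal correlation between visits; attrition taken as complete loss, so 200 × 0.8 = 160 per arm (320 in total).

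**Formula.** With SD 1, SE = √(2v/n), where n is the number per arm and v depends on the contrast. Power = Φ(0.30/SE − 1.96). Detectable difference at 80% power = 2.80 × SE.

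**1. Trying to reproduce the stated 80% (single visit, v = 1)**
- n = 200: SE = 0.100, power = Φ(3.00 − 1.96) = 85.1% (t-test 84.9%), detectable d = 0.28.
- n = 160: SE = √(2/160) = 0.1118, power = Φ(2.683 − 1.96) = 76.5% (t-test 76.3%), detectable d = 0.31.
- Exactly 80% at d = 0.30 needs about 175 analysed per arm, which is a loss of 1 − 175/200 = 12.5%.
- Taken literally, d = 30 gives power of essentially 100%.

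The stated 80% is therefore not reproduced by either count.

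**2. Trying the form that fits the parallel calculation.** The white, non-Hispanic Aim 1 figures (0.17, 0.50, 0.84 for SD 1, 3, 5) are matched by a slope per visit with correlation 0.1 and 250 per arm: v = (1 − 0.1)/2 = 0.45, SE = √(0.90/250) = 0.060, and 2.80 × 0.060 = 0.168, times 3 = 0.504, times 5 = 0.840. That match leaves out the 20% attrition. The same form gives 0.188 SD per visit with 200 per arm and 0.210 with 160, so it does not yield 0.30 either.

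**3. The planned interaction, with 0.30 SD as the difference at month 9 and n = 160**
- End-minus-baseline change: v = 2(1 − ρ). At ρ = 0.1, SE = √(3.6/160) = 0.150.
- Linear slope over 0, 3, 9 months, scaled to month 9: the mean time is 4 and the sum of squares is 16 + 1 + 25 = 42, so v = (81/42)(1 − ρ). At ρ = 0.1, SE = 0.147.

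| ρ | Change: power | Change: detectable | Slope: power | Slope: detectable |
|---|---|---|---|---|
| 0.1 | 51.6% | 0.42 | 53.1% | 0.41 |
| 0.5 | 76.5% | 0.31 | 78.0% | 0.31 |
| 0.7 | 93.4% | 0.24 | 94.2% | 0.24 |

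Solving 0.30/SE = 2.80 gives ρ = 0.54 for the change and 0.52 for the slope. With no attrition at all (n = 200), power at ρ = 0.1 is still only 60.9% and 62.4%.

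**4. Contrasts that exceed 80% (n = 160)**
- Mean of the two follow-ups, v = (1 + ρ)/2: 95.1% at ρ = 0.1, 87.3% at 0.5, 82.9% at 0.7. It crosses 80% near ρ = 0.83.
- A slope difference of 0.30 SD per visit: 97.9% at ρ = 0.1. Over two visit steps this means 0.60 SD at the last visit, a larger effect than the text describes.

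**The case against.** The strongest reply is that 76% is a single-visit t-test figure, whereas the plan analyses repeated measures. The white, non-Hispanic paragraph shows that the team allowed for them, and power after attrition at ρ = 0.1 runs from about 52% to 98% depending on what d = 0.30 describes. This stands: 76% must not be presented as the power of the planned test. It does not rescue the sentence, because the contrasts that clear 80% easily are the follow-up average, which is not the interaction, and a per-visit slope that implies twice the effect.

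The H/L Aim 1 sentence does not mention attrition, and without it d = 0.30 has 85% power at one visit, which satisfies a claim of at least 80%. However, the plan says "and estimate study attrition of 20" percent for the same people under Aim 2, and its retention paragraph covers both populations. It is also fair that a participant lost after the 3-month survey still contributes data under the intention-to-treat GEE, so 160 per arm is somewhat pessimistic.

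The d = 30 may be a typing slip or a decimal point lost when the PDF was read. Either way it needs only a check and, if printed that way, a correction. On the single-visit view the gap is also small, 0.31 against 0.30.

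A reader might infer from the Randomization section, which gives 100 H/L participants per arm, that power is only 47-56%. The documents do not support that. The Project Description sets 400 H/L participants at each of two sites, 200 of them high risk, and the power section states 400 high risk in total. The 100 per arm is therefore a per-site count.

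**Conclusion.** The concern holds in this form. The printed effect size cannot be right. Read as 0.30, the 80% is unsupported on the plan's own attrition and main test: about 76% at a single visit, about 52-53% for the interaction at the only correlation that the plan gives, and 77-78% at 0.5. For the interaction, 80% requires a correlation of roughly 0.54 or more under the end-minus-baseline form.

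A reader might conclude that the H/L sample is demonstrably too small. That goes too far. The documents give neither the contrast nor an H/L correlation, and a correlation of 0.7 or a follow-up average would bring power above 80%.

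These figures rest on alpha 0.05, d = 0.30, equal between-visit correlation, complete loss of 20%, and a normal approximation without covariate adjustment.

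**What to change.** Check the source and, if d is printed as 30, correct it to 0.30. Replace the H/L Aim 1 sentence with one that states:
- 400 high-risk participants randomised and 320 evaluable after 20% attrition;
- two-sided alpha 0.05, if that is what was intended;
- the contrast to which the effect refers (for example, the between-arm difference in change to month 9 under the GEE interaction);
- power or detectable difference for that contrast over a range of within-person correlations such as 0.1 to 0.7. On the end-minus-baseline form, the detectable difference runs from 0.42 to 0.24 SD.

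If a single-visit figure is kept, label it as such: 76% at d = 0.30, 80% at d = 0.31. The cost is one recalculated paragraph. No added enrolment or design change is needed.
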